5.1.8.2. Adverse Events of Special Interest

AESIs will be listed and summarized by treatment group based on the SAF-LTS. Differences in event rate for AESIs between fasinumab and placebo will be estimated using exact binomial confidence intervals.

Radiograph data related to AA including change from baseline in joint space width will be summarized by SAF over time. Within index type, Knee Society Score questionnaire or Harris Hip Score questionnaire results will be listed.

5.1.8.3. Clinical Laboratory Measurements

Laboratory test results will be summarized by baseline and change from baseline to each scheduled assessment time with descriptive statistics based on the SAF-LTS by treatment group and combined fasinumab group.

Shift tables based on baseline normal/abnormal and other tabular and graphical methods may be used to present the results for laboratory tests of interest.

Listings will be provided with flags indicating the out of laboratory range values.

A Treatment-Emergent Potential Clinically Significant abnormal value (PCSV) is a laboratory value that was normal at Screening and Baseline but became abnormal and met PCSV criteria after treatment with study drug. Definition of PCSV is listed in [Appendix 11.2](#). Treatment Emergent Potentially clinically significant values (PCSVs) will be summarized based on the SAF-LTS by treatment group and combined fasinumab group. Additional exploratory analyses using alternative cut-points may be conducted.

For hs-CRP, plots of means and medians of the observed values and change from baseline over time will presented by treatment group.

For hs-CRP, subgroup analysis will be performed for the following:

- Baseline hs-CRP ([0 – 3], [>3 -10], [>10])
- Adjudicated Arthropathy category 1 (patients without / with AA)
- Adjudicated Arthropathy category 2 (patients without AA, patients with RPOA-1, and patients with non-RPOA-1 AA)
- Destructive Arthropathy category (patients without AA, patients with non-DA AA, patients with DA)

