#### 4.2.3. Exclusion Criteria

A patient who meets any of the following criteria will be excluded from the study:

1. History or presence at the screening visit of non-OA inflammatory joint disease (eg, rheumatoid arthritis, lupus erythematosus, psoriatic arthritis, pseudogout, gout, spondyloarthropathy, polymyalgia rheumatica, joint infections within the past 5 years), Paget's disease of the spine, pelvis or femur, neuropathic disorders, multiple sclerosis, fibromyalgia, tumors or infections of the spinal cord, or renal osteodystrophy
2. History or presence on imaging of arthropathy (osteonecrosis, subchondral insufficiency fracture, rapidly progressive osteoarthritis type 1 or type 2), stress fracture, recent stress fracture, neuropathic joint arthropathy, hip dislocation (prosthetic hip dislocation is eligible), knee dislocation (patella dislocation is eligible), congenital hip dysplasia with degenerative joint disease, extensive subchondral cysts, evidence of bone fragmentation or collapse, or primary metastatic tumor with the exception of chondromas or pathologic fractures during the screening period
3. Signs or symptoms of carpal tunnel syndrome within 6 months of screening

4. Patient is not a candidate for MRI
5. Is scheduled for a joint replacement surgery to be performed during the study period
6. Systemic (ie, oral or intramuscular) corticosteroids within 30 days prior to the screening visit. Intra-articular corticosteroids in the index joint within 12 weeks prior to the screening visit, or to any other joint within 30 days prior to the screening visit (topical, intra-nasal, and inhaled corticosteroids are permitted)
7. History or presence at the screening visit of autonomic neuropathy, diabetic neuropathy, or other peripheral neuropathy, including reflex sympathetic dystrophy
8. History or diagnosis of chronic autonomic failure syndrome including pure autonomic failure, multiple system atrophy (Shy-Drager syndrome)
9. Poorly controlled diabetes (defined as any single value of hemoglobin A1c [HbA1c] >9.0%) at the screening visit
10. Known history of human immunodeficiency virus infection
11. Known history of ocular herpes simplex virus, herpes simplex virus pneumonia, or herpes simplex virus encephalitis
12. History of sickle cell disease, including S-C disease and S- $\beta$  thalassemia
13. Confirmed elevated screening alanine aminotransaminase (ALT) or aspartate aminotransaminase (AST)  $\geq 2.5$  times the ULN

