5.1.7. Analysis of Safety Data

The analysis of safety and tolerability will be performed on the SAF-LTS, as defined in Section 3.2.

The safety analysis will be based on the reported AEs and other safety information (clinical laboratory evaluations, vital signs, 12-lead ECG, Physical Examination, etc.).

Treatment-Emergent Potential Clinically Significant Values (PCSV) in laboratory variables, vital signs and ECG are defined in [Appendix 11.2](#).

Period of observation: The observation period will be divided into three segments: pre-treatment, on-treatment and post-treatment.

- The pre-treatment period is defined as the time between when the patients give informed consent and the start of study drug.
- The LTS on-treatment period is defined as the time from first dose of study drug up to 28 days after the last dose of study drug. The LTS post-treatment period is defined as the time starting 29 days after last dose of study drug (after the on-treatment period) to up to 24 weeks post the last dose of study drug (up to week 72).

Day 1 is the first day of study drug, Day -1 is the day before Day 1, and there is no Day 0.

The time interval to detect any on-treatment event or abnormality is between the first dose of double-blind study drug injection and the end of treatment plus 28 days. Data collected outside this interval will be excluded from the estimation of descriptive statistics and identification of abnormalities for laboratory evaluations, ECGs and vital signs. All post-baseline data during the interval will be using in the PCSV analysis including scheduled and unscheduled assessments.

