
Laboratory Safety Variables below LLOQ or above ULOQ

For central laboratory data below the lower limit of quantification (LLOQ), half of the lower limit value (i.e., LLOQ/2) will be used for quantitative analyses.

Missing laboratory, ECG, vital sign, physical exam, neurological exam

No imputations for missing laboratory data, ECG data, vital sign data, physical examination, or neurological examination data will be made.

Handling of Potentially Clinically Significant Abnormalities

If a patient has a missing baseline value they will be grouped in the category “normal/missing at baseline”.

For PCSAs with 2 conditions, one based on a change from baseline value and the other on a threshold value or a normal range, with the first condition being missing, the PCSA will be based only on the second condition.

For a PCSA defined on a threshold and/or a normal range, this PCSA will be derived using this threshold if the normal range is missing; eg, for eosinophils the PCSA is >0.5 GIGA/L or >ULN if ULN \geq 0.5 GIGA/L. When ULN is missing, the value 0.5 should be used.

Measurements flagged as invalid by the laboratory will not be summarized or taken into account in the computation of PCSA values.

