Adverse events	X	X
Vital signs	X	X
Orthostatic blood pressure ⁴	X	X
Physical examination with joint exam	X ¹	X
Medical history related to the joint replacement	X	X
Joint pain questionnaire	X	X
Post-operative assessment questionnaire ²	X	X
Bilateral radiograph (knee, hip, shoulder) ⁵	X ⁶	X
Event-triggered imaging ³	X	X

F/U: Follow-up

- All available information for patients who undergo JR surgery must be collected, including placement of the prosthesis, healing of the surgical wound, and the results of the histopathologic examination.
- Knee Society Score questionnaire for knee replacements or Harris Hip Score questionnaire for hip replacements.
- Imaging (x-ray and/or MRI) will be performed on any joint following a report of clinically significant worsening or exacerbation of pain in that joint.
- If it is not possible to obtain orthostatic blood pressure following JR then blood pressure and pulse should be recorded.
- In the event of more than 1 JR, imaging assessments should be repeated if it has been >60 days since the joints were last imaged. If it has been ≤60 days since imaging assessments were completed, imaging assessments may be completed at the discretion of the investigator. An MRI may be requested by the imaging vendor after review of the x-rays.
- Imaging will be done at week 4 if not done pre-operatively.

11.2. Reference for Criteria for Treatment-Emergent Potentially Clinically Significant Values (PCSV)

The PCSV criteria below should be used as a reference; the actual criteria for each study should be determined and agreed to by the study team prior to database lock as part of SAP and should be based on the study population, indication, and potential effects of study treatment.

Table 2: Criteria for Treatment-Emergent Potentially Clinically Significant Values (PCSV)

Parameter	Treatment Emergent PCSV	Comments
Clinical Chemistry		
ALT*	>3 and ≤ 5 ULN and baseline ≤ 3 ULN*	Enzyme activity must be expressed in ULN, not in IU/L.
	>5 and ≤ 10 ULN and baseline ≤ 5 ULN	FDA DILI Guidance July 2009.
	>10 and ≤ 20 ULN and baseline ≤ 10 ULN	Each category is calculated independently.
	>20 ULN and baseline ≤ 20 ULN	* At least one level is required; multiple levels are optional for phase 2/3 studies. If it is desirable to get the distribution across the different PCSV levels, additional shift table on ≤3, >3 to ≤5, >5 to ≤10, >10 to ≤20, and >20 category for baseline vs. post baseline may be provided

Parameter	Treatment Emergent PCSV	Comments

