AST*	
>3 and ≤ 5 ULN and baseline ≤ 3 ULN*
 
>5 and ≤ 10 ULN and baseline ≤ 5 ULN
 
>10 and ≤ 20 ULN and baseline ≤ 10 ULN
 
>20 ULN and baseline ≤ 20 ULN
	
Enzyme activity must be expressed in ULN, not in IU/L.
 
FDA DILI Guidance July 2009.
 
Each category is calculated independently.
 
* At least one level is required; multiple levels are optional for phase 2/3 studies. If it is desirable to get the distribution across the different PCSV levels, additional shift table on ≤3, >3 to ≤5, > 5 to ≤10, >10 to ≤20, and >20 category for baseline vs. post baseline may be provided

Alkaline Phosphatase	>1.5 ULN and baseline ≤ 1.5 ULN	
Enzyme activity must be expressed in ULN, not in IU/L.
 
FDA DILI Guidance July 2009.

Total Bilirubin*	
>1.5 and ≤ 2 ULN and baseline ≤ 1.5 ULN*
 
>2 ULN and baseline ≤ 2.0 ULN
	
Must be expressed in ULN, not in μmol/L or mg/L. Categories are cumulative.
 
FDA DILI Guidance July 2009.
 
* At least one level is required; multiple levels are optional for phase 2/3 studies. If it is desirable to get the distribution of significant level, additional shift table on ≤1.5, >1.5 to ≤2.0 and > 2.0 category for baseline vs. post baseline may be provided

Conjugated Bilirubin	(Direct Bilirubin >35% Total Bilirubin and Total Bilirubin >1.5 ULN) and (Direct Bilirubin ≤35% Total Bilirubin or Total Bilirubin ≤1.5 ULN) at baseline	Conjugated bilirubin dosed on a case-by-case basis.

Parameter	Treatment Emergent PCSV	Comments
ALT/AST and Total Bilirubin	
(ALT >3 ULN and TBILI>2 ULN) and baseline (ALT <=3 ULN or TBILI <=2 ULN)
 
(AST >3 ULN and TBILI>2 ULN) and baseline (AST <=3 ULN or TBILI <=2 ULN)
 
(ALT >3 ULN and TBILI>1.5 ULN) and baseline (ALT <=3 ULN or TBILI <=1.5 ULN)
 
(AST >3 ULN and TBILI>1.5 ULN) and baseline (AST <=3 ULN or TBILI <=1.5 ULN)
	FDA DILI Guidance July 2009.
ALT/AST and Total Bilirubin and ALP	
(ALT >3 ULN and TBILI>2 ULN and ALP < 2 ULN) and baseline (ALT <=3 ULN or TBILI <=2 ULN or ALP >=2 ULN)
 
(AST>3 ULN and TBILI>2 ULN and ALP < 2 ULN) and baseline (AST <=3 ULN or TBILI <=2 ULN or ALP >=2 ULN)
	FDA DILI Guidance July 2009.

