CPK*	
>3 and ≤ 10 ULN and baseline ≤ 3ULN*
 
>10 ULN and baseline ≤ 10ULN
	
FDA Feb 2005.
 
Am J Cardiol April 2006.
 
Categories are cumulative.
 
* At least one level is required; multiple levels are optional for phase 2/3 studies. If it is desirable to get the distribution of significant level, additional shift table on ≤3, >3 to ≤10, and > 10 category for baseline vs. post baseline may be provided

Parameter	Treatment Emergent PCSV	Comments
Creatinine	$\geq 150 \mu\text{mol/L}$ (Adults) and baseline $< 150 \mu\text{mol/L}$ $\geq 30\%$ change from baseline and $< 100\%$ change from baseline $\geq 100\%$ change from baseline	Benichou C., 1994 3 independent criteria
Uric Acid		Harrison - Principles of internal Medicine 17 th Ed., 2008.
Hyperuricemia	$> 408 \mu\text{mol/L}$ and $\leq 408 \mu\text{mol/L}$ at baseline	Two independent criteria
Hypouricemia	$< 120 \mu\text{mol/L}$ and $\geq 120 \mu\text{mol/L}$ at baseline	
Blood Urea Nitrogen	$\geq 17 \text{ mmol/L}$ and $< 17 \text{ mmol/L}$ at baseline	Two independent criteria
Chloride		Two independent criteria
Hypochloremia	$< 80 \text{ mmol/L}$ and baseline $\geq 80 \text{ mmol/L}$	
Hyperchloremia	$> 115 \text{ mmol/L}$ and baseline $\leq 115 \text{ mmol/L}$	
Sodium		Two independent criteria
Hyponatremia	$\leq 129 \text{ mmol/L}$ and baseline $> 129 \text{ mmol/L}$	
Hypernatremia	$\geq 160 \text{ mmol/L}$ and baseline $< 160 \text{ mmol/L}$	
Potassium		FDA Feb 2005.
Hypokalemia	$< 3 \text{ mmol/L}$ and baseline $\geq 3 \text{ mmol/L}$	Two independent criteria
Hyperkalemia	$\geq 5.5 \text{ mmol/L}$ and baseline $< 5.5 \text{ mmol/L}$	
Total Cholesterol	$\geq 7.74 \text{ mmol/L}$ and $< 7.74 \text{ mmol/L}$ at baseline	Threshold for therapeutic intervention.

[figure not shown]
Parameter	Treatment Emergent PCSV	Comments
Triglycerides	≥4.6 mmol/L and < 4.6 mmol/L at baseline	Threshold for therapeutic intervention.
Glucose		
Hypoglycaemia	(≤3.9 mmol/L and <LLN) and (>3.9 mmol/L or ≥LLN) at baseline	ADA May 2005.
Hyperglycaemia	≥11.1 mmol/L (unfasted); ≥7 mmol/L (fasted) and < 11.1 mmol/L (unfasted); <7 mmol/L (fasted) at baseline	ADA Jan 2008.
HbA1c	>8% and ≤ 8% at baseline	
Albumin	≤25 g/L and >25 g/L at baseline	
hs-CRP	2 ULN or > 10 mg/L (if ULN not provided)	FDA Sept. 2005
Hematology		

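### SAP 5.1.8.3 requires normal screening and baseline values before a laboratory PCSV counts as treatment-emergent; this contradicts SAP 5.1.7 and Appendix 11.2 and, applied literally, undercounts the PCSV summary

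*SAP*

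**What the plan says.** SAP 5.1.8.3 describes a treatment-emergent laboratory PCSV as a value that "was normal at Screening and Baseline but became abnormal and met PCSV criteria after treatment with study drug". Its next sentence, "Definition of PCSV is listed in" Appendix 11.2, sends the reader to the table of criteria.

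SAP 5.1.7 points to the same place without any normality condition: "Treatment-Emergent Potential Clinically Significant Values (PCSV) in laboratory variables, vital signs and ECG are defined in" Appendix 11.2. SAP 4.5.4 also refers to that appendix for the definitions.

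Appendix 11.2, Table 2, is titled as the criteria for treatment-emergent PCSVs and carries its own baseline conditions. The lowest ALT level is ">3 and ≤ 5 ULN and baseline ≤ 3 ULN", alkaline phosphatase is ">1.5 ULN and baseline ≤ 1.5 ULN", and the upper CPK level is ">10 ULN and baseline ≤ 10ULN". No row mentions screening. The creatinine percent-change criteria, the hemoglobin fall of 20 g/L or more, and hs-CRP have no condition on the baseline level.

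On missing data, SAP 6.3 says: "If a patient has a missing baseline value they will be grouped in the category" of normal or missing at baseline. No section says which definition prevails where they differ.

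Protocol 4.2.3, exclusion criterion 13, removes patients only when a confirmed screening ALT or AST is at least 2.5 x ULN.

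**The concern.** Two rules carry the same name and select different patients. The text rule needs a value inside the normal range at two time points. For most analytes the appendix rule needs only a baseline that has not already passed the PCSV threshold. Patients between the upper limit of normal and the threshold count under one rule and not under the other.

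What is at stake is the treatment-emergent PCSV table for laboratory data. Two programmers working correctly from this SAP could produce different tables. If the 5.1.8.3 sentence were followed, some on-treatment threshold crossings would not be counted, including large ones, because of a mild abnormality at entry.

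**Working it through.** The documents state no PCSV rate or other figure that depends on this definition, so there is nothing to reproduce. The check applies both rules to the same patients.

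**Rules.** ALT is in multiples of ULN, and normal is read as at or below 1 x ULN.
- Text rule (SAP 5.1.8.3): screening ≤ 1, baseline ≤ 1, and an on-treatment value meeting a PCSV criterion.
- Appendix rule (Appendix 11.2, ALT rows): >3 to 5 with baseline ≤ 3; >5 to 10 with baseline ≤ 5; >10 to 20 with baseline ≤ 10; >20 with baseline ≤ 20.

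**Example patients.** All are below the 2.5 x ULN exclusion limit at screening.

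| Screening | Baseline | On treatment | Appendix rule | Text rule |
|---|---|---|---|---|
| 0.8 | 0.9 | 3.5 | counts | counts |
| 1.4 | 1.2 | 3.5 | counts | not counted |
| 1.5 | 1.5 | 6 | counts | not counted |
| 2.4 | 2.4 | 12 | counts | not counted |
| 2.0 | 0.9 | 6 | counts | not counted |

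The last patient fails the text rule on screening alone. Such cases should be uncommon. Protocol Table 1 schedules chemistry and hematology at screening and not again before dosing, so screening and baseline will usually be one sample. They differ when a screening test is repeated, which Protocol 6.2.1 allows.

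**Can the two rules be read together?** No. If every counted patient had to start at or below 1 x ULN, the appendix limits of baseline ≤ 3, ≤ 5, ≤ 10 and ≤ 20 x ULN would never exclude anyone. The change-only criteria also conflict. A patient whose hemoglobin is out of range at entry and falls by 20 g/L or more counts under the appendix and not under the text.

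**Who is affected?** Patients already past a threshold at baseline are excluded from that level under both rules. For threshold criteria, the difference is therefore confined to patients out of range but below the threshold at entry. For elevation criteria these patients are arithmetically closer to it: passing 3 x ULN takes a rise of more than 3/1.0 = 3.0-fold from 1.0 x ULN, but only 3/2.4 = 1.25-fold from 2.4 x ULN.

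**Size.** Let f be the share of patients out of range but below threshold at entry, and RR their risk of a PCSV relative to other patients. The share of appendix-rule events lost under the text rule is f·RR / (f·RR + 1 − f). The documents give neither input. With assumed values:
- f = 5%, RR = 1: 0.05 / (0.05 + 0.95) = 5%
- f = 10%, RR = 3: 0.30 / (0.30 + 0.90) = 25%
- f = 10%, RR = 4: 0.40 / (0.40 + 0.90) = 31%
- f = 20%, RR = 10: 2.00 / (2.00 + 0.80) = 71%

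A spread of 5% to 71% reflects only the choice of assumptions, so no single figure should be quoted.

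**The case against.** The best defence is that the appendix is the working definition and the 5.1.8.3 sentence only a loose paraphrase. SAP 4.5.4, SAP 5.1.7 and the sentence after the disputed one all point to Appendix 11.2. This largely stands as a guide to intent, but it does not resolve the text. The appendix calls itself a reference whose final criteria are to be settled as part of the SAP, no other list is given, and 5.1.8.3 still states a stricter rule in plain words.

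A second defence is that nothing is hidden. SAP 5.1.8.3 commits to change-from-baseline summaries by visit and to listings that flag out-of-range values, and it allows shift tables. Abnormalities that are symptomatic, need treatment or lead to discontinuation are recorded as adverse events. This stands too: a reader might infer that these patients vanish from the safety evaluation, and they do not. Even so, the shift tables are optional and none of these outputs replaces the PCSV count.

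Third, the missing-baseline category in SAP 6.3 might suggest tabulation by baseline status, with abnormal-baseline patients shown separately. The SAP does not commit to that layout. The convention is also not part of the contradiction, since it governs missing values only.

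Finally, a reader might infer that the primary safety endpoint is compromised. The documents do not support that. The laboratory component in SAP 4.5.1 is change from baseline, which SAP 5.1.7.1 summarizes descriptively. PCSV counts are not named there, and the disputed sentence leaves those summaries unchanged.

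**Conclusion.** The contradiction is real and should be removed. Under the literal 5.1.8.3 rule, the laboratory PCSV table omits eligible patients who were out of range but below threshold at entry and then crossed it, at whatever level they reach. The direction is a lower count. The size cannot be determined from the documents.

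Three stronger readings are not supported. One is that a quarter to a third of events are lost: that needs an assumed 10% of patients out of range and a three- to fourfold risk, neither of which the documents give. Another is that the omitted patients are those most at risk: the documents give no risk by baseline status, and the proximity argument holds for elevation thresholds but does not carry over automatically to change-from-baseline criteria. The third is bias between arms: the same rule applies to all of them, and nothing in the documents shows a differential effect.

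The conclusion rests on reading normal as within the laboratory reference range and on taking Appendix 11.2 as the operative list.

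**What to change.** In SAP 5.1.8.3, delete the opening condition of the quoted definition, so that neither a normal screening value nor a normal baseline value is required. State instead that a treatment-emergent laboratory PCSV is a value within the SAP 5.1.7 on-treatment window (first dose to 28 days after the last dose) that meets the full Appendix 11.2 row, including that row's own baseline condition where it has one, with missing baselines handled under Section 6.3.

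Three details of this wording matter:
- The window must be named, because an open-ended reference to post-dose values would go beyond SAP 5.1.7.
- The rule must refer to the full row. Asking only that baseline did not meet the criterion could count an ALT falling from 6 to 4 x ULN as new, since 6 lies outside the >3 to 5 band; the row's own condition of baseline ≤ 3 x ULN excludes it.
- The phrase on rows that have a baseline condition is needed because the change-only criteria do not have one.

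The cost is one SAP sentence, settled before database lock. It needs no new data and has no effect on sample size or multiplicity.

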5.1.8.4. Analysis of Vital Signs

Vital signs (temperature, pulse, blood pressure, orthostatic blood pressure/heart rate, and respiration rate) will be summarized by baseline and change from baseline to each scheduled assessment time with descriptive statistics by treatment group and combined fasinumab for the SAF-LTS.

PCSV summary including orthostatic hypotension will be constructed for on-treatment period, post-treatment period and overall during the LTS study.

5.1.8.5. Analysis of 12-Lead ECG

ECG parameters (Ventricular Rate, PR Interval, QRS Interval, QT Interval, RR Interval, QTcF QTcB interval) will be summarized by baseline and change from baseline to each scheduled and collected assessment time. PCSV summary of ECG parameters will be provided for on-treatment period (for LTS study), post-treatment period, and overall for the SAF-LTS.

ECG status (i.e. normal, abnormal) will be reported. Shift tables will be provided to present the post-baseline status according to the baseline status (normal or missing / abnormal) by treatment.

